7.2. Data Monitoring Committee

The specific activities of the DMC will be governed by a charter that will define the DMC's membership, meeting frequency, procedures/conduct, and requirements for reporting its observations and recommendations to the sponsor.

To ensure safety oversight throughout the study, a DMC will review safety and preliminary efficacy data and provide recommendations to the sponsor as described below.

The DMC will convene at the following times and for the following activities during the study:

- Review safety data for at least 5 subjects who received IMR-687 at the lower dose and make recommendation as to the inclusion of the higher dose.
- Review safety data to confirm acceptable safety and tolerability of the higher dose of IMR-687 and make recommendation as to whether the dose levels could be modified.
- Review safety data on a periodic basis as defined in the DMC charter. For example, results of blinded laboratory tests will be communicated to the investigator if a subject's absolute reticulocyte count declines to $<80 \times 10^9/L$, Hb declines to $<5.0 \text{ g/dL}$, or Hb declines to $\geq 3 \text{ g/dL}$ from baseline (Day 1) (but this does not require breaking of the treatment assignment blind). This is to ensure subject safety by allowing the investigator to monitor relevant safety data.
- At any time during the study – upon request by the sponsor, medical monitor, or DMC – should a concern arise from emerging safety data for which DMC review and assessment is desired. This includes the emergence of a frequency or pattern of AEs or SAEs that suggest an unexpected or otherwise concerning safety signal. At any time, the DMC may recommend to stop a dose arm or the study.

The DMC may review the following subject data, depending on the scope of the meeting, and may recommend to continue the study as planned, modify the study, or terminate the study for safety concerns:

- Unblinded safety, PK, and preliminary efficacy/PD data, which may include TEAEs, SAEs, PK data, clinical laboratory test results, vital signs, and other relevant data for all subjects randomized.
- Additionally, the DMC chairperson will receive copies of all SAE reports for ongoing review during the study. The DMC chairperson may forward the SAE reports to the full DMC if he/she feels that their immediate input on, or awareness of, the SAE would be helpful.

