8. SELECTION AND WITHDRAWAL OF SUBJECTS

8.1. Subject Inclusion Criteria

Each subject must meet all the following criteria to be enrolled in the study:

1. Male or female aged ≥ 18 to ≤ 65 years at the time of ICF signing.
2. Confirmed diagnosis of SCD (HbSS, HbS β^0 thalassemia, or HbS β^+ thalassemia) in the medical record; if not available, the diagnosis must be confirmed at the site's local laboratory instead.
3. Subjects must have had at least 2 and no more than 12 documented episodes of VOC in the past 12 months at the time of ICF signing and at randomization (Day 1).

For study eligibility, VOC is defined as a documented episode of an acute painful crisis (for which there was not an explanation other than VOC) that involved moderate to severe pain lasting for at least 2 hours and at least one of the following:

- Use of escalated analgesia (including healthcare professional-instructed use of an analgesic prescription)
- A hospital, emergency department, or clinic visit and/or healthcare telephone consultation at the time of occurrence
- Diagnosis of ACS (defined as an acute illness characterized by fever and/or respiratory symptoms, accompanied by a new pulmonary infiltrate on a chest X-ray), hepatic sequestration, splenic sequestration, or priapism (in males)

4. Hb of >5.5 and <10.5 g/dL; Hb values within 21 days post-transfusion will be excluded.
5. *This inclusion criterion has been removed.*
6. Subjects receiving HU must have received it continuously for at least 6 months prior to signing the ICF, and must have been on a stable dose for at least 3 months prior to signing the ICF, with no anticipated need for dose adjustments during the study including the screening period, in the opinion of the investigator.
7. Female subjects must not be pregnant or breastfeeding and be highly unlikely to become pregnant. Male subjects must be unlikely to impregnate a partner. Male or female subjects must meet at least one of the following criteria:

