9.2 Safety Endpoints

Safety endpoints include the number and percentage of subjects with the following:

- At least one treatment-emergent adverse events (AEs)
- At least one treatment-emergent serious adverse events (SAEs)
- At least one clinically significant change in a laboratory test parameter
- At least one clinically significant change in a vital signs parameter
- At least one clinically significant change in an electrocardiogram (ECG) parameter

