13.5.8.2 Laboratory Data

Clinical laboratory tests (serum chemistry, hematology, urinalysis, and specialty hematology) will be summarized using the safety analysis set. Results will be evaluated and presented using the International System of Units (SI units) unless otherwise stated. Clinical laboratory values will be graded from Grade 1 to Grade 4 using NCI CTCAE, version 5.0. Post-baseline laboratory values will only be compared to baseline values from the same source. For example, if the baseline value for a parameter came from a local laboratory, post-baseline results from the same local laboratory should be used for the analysis.

Hematology assessments include: RBC count (mean corpuscular volume [MCV], mean corpuscular Hb, and mean corpuscular Hb concentration), hematocrit, Hb, platelets, WBC count (with differential: basophils, eosinophils, neutrophils, monocytes, and lymphocytes), erythrocyte count, and reticulocyte count and reticulocyte percentage. Some of these assessments are also considered PD endpoints, and further detailed in the secondary and exploratory endpoint sections above.

Specialty hematology assessments include: HbF and percent F-cells.

Coagulation assessments include: PT, aPTT, and international normalized ratio (INR).

Serum chemistry assessments include: alanine aminotransferase (ALT), albumin, alkaline phosphatase (ALP), aspartate aminotransferase (AST), bicarbonate, blood urea nitrogen (BUN), chloride, calcium, creatinine, glucose, lactate dehydrogenase (LDH), sodium, potassium, magnesium, phosphate, bilirubin (total, direct, and indirect), creatine kinase, total protein, glomerular filtration rate (GFR), and gamma-glutamyl transferase (GGT). Follicle stimulating hormone (FSH) will be included as well, but this is only collected for post-menopausal women at screening. Some of these assessments are also considered PD endpoints, and further detailed in the secondary and exploratory endpoint sections above.

Urinalysis assessments include: appearance, color, pH, specific gravity, ketones, protein, glucose, bilirubin, and urobilinogen, including occult blood and microscopic examination of sediment (only if occult blood is detected).

The laboratory results and change from baseline will be summarized by visit by treatment group for central laboratory continuous hematology, serum chemistry and urinalysis parameters separately. Note that character urinalysis tests will only be listed.

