Shift tables representing the shift from the baseline grade to maximum NCI-CTCAE Grades (Grade I to IV and Missing) will be provided for selected hematology and chemistry parameters by visit by treatment group. See [Appendix 5](#) for details.

Potentially clinically significant (PCS) Criteria for hepatic function and renal function are shown in [Table 9](#) below. The number and percentage of subjects meeting these PCS criteria will be summarized for hepatic function parameters (ALT, AST, ALP, and total bilirubin) and the renal function parameter (serum creatinine) separately. Any subject with any post-baseline result (including “unscheduled” visits) meeting the criteria will be included in the tabulation.

Table 9 PCS Criteria for Hepatic Function and Renal Function

| Hepatic Function | Renal Function |
|--|---|
| 
 ○ Post-baseline Alanine Aminotransferase (ALT) $\geq 3 \times$ upper limit of normal (ULN) ○ Post-baseline Aspartate Aminotransferase (AST) $\geq 3 \times$ ULN ○ Post-baseline Direct Bilirubin (BILDIR) $\geq 2 \times$ ULN ○ Post-baseline ALT/AST and BILDIR (ALT $\geq 3 \times$ ULN or AST $\geq 3 \times$ ULN) and BILDIR $\geq 2 \times$ ULN (Hy's Law) | 
 ○ Post-baseline Creatinine Clearance (CREATCLR) $< 0.5 \times$ baseline ○ Post-baseline Serum Creatinine (CREAT) $> 2 \times$ baseline |

Creatinine clearance are not directly collected and will be calculated using the Crockroft Gault formula:

$$CrCl = \frac{(140 - \text{patient's age in years}) \times \text{Body weight in kg}}{72 \times \text{serum creatinine in mg/dl}}$$

All laboratory parameters (serum chemistry, central laboratory hematology, local laboratory hematology, specialty hematology, coagulation, and urinalysis) will be displayed in individual subject data listings.

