| Blood bicarbonate decreased | <LLN and no intervention initiated | | | |
| Blood lactate dehydrogenase increased | >ULN | | | |
| Hemoglobin increased (a) | Increase in >0 – 2 gm/dL above ULN (a) | Increase in >2 – 4 gm/dL above ULN (a) | Increase in >4 gm/dL above ULN (a) | n/a |
| Anemia (hemoglobin decreased) | LLN- 10g/dL; <LLN – 6.2 mmol/L; <LLN – 100 g/L | <10.0 – 8.0 g/dL; <6.2 – 4.9 mmol/L; <100 – 80g/L | <8.0 g/dL; <4.9 mmol/L; <80 g/L; transfusion indicated | Life-threatening consequences; urgent intervention indicated |
| INR increased | >1.2 – 1.5; >1 -1.5 x baseline if on anticoagulation (use of anticoagulation identified using the B01A ATC code) | >1.5 – 2.5; >1.5 – 2.5 x baseline if on anticoagulation (use of anticoagulation identified using the B01A ATC code) | >2.5; >2.5 x baseline if on anticoagulation (use of anticoagulation identified using the B01A ATC code) | - |
| Eosinophilia | >ULN and >Baseline | | Steroids initiated | |
| Neutrophil count decreased | <LLN - 1500/mm3; <LLN - 1.5 x 10e9 /L | <1500 - 1000/mm3; <1.5 - 1.0 x 10e9 /L | <1000 - 500/mm3; <1.0 - 0.5 x 10e9 /L | <500/mm3; <0.5 x 10e9 /L |
| Lymphocyte count decreased | <LLN - 800/mm3; <LLN - 0.8 x 10e9/L | <800 - 500/mm3; <0.8 - 0.5 x 10e9 /L | <500 - 200/mm3; <0.5 - 0.2 x 10e9 /L | <200/mm3; <0.2 x 10e9 /L |
| Lymphocyte count increased | - | >4000/mm3 - 20,000/mm3 | >20,000/mm3 | - |

| Investigations | | | | |
|--|---|---|---|---|
| Laboratory Analyte | Grade | | | |
| | 1 | 2 | 3 | 4 |
| Leukocytosis (White blood cell increased) | | | >100,000/mm ³ | Clinical manifestations of leucostasis (sic); urgent intervention indicated Note that the spelling is often "leukostasis" in the literature. |
| Platelet count decreased | <LLN - 75,000/mm ³ ; <LLN - 75.0 x 10 ⁹ /L | <75,000 - 50,000/mm ³ ; <75.0 - 50.0 x 10 ⁹ /L | <50,000 - 25,000/mm ³ ; <50.0 - 25.0 x 10 ⁹ /L | <25,000/mm ³ ; <25.0 x 10 ⁹ /L |
| White blood cell decreased | <LLN - 3000/mm ³ ; <LLN - 3.0 x 10 ⁹ /L | <3000 – 2000/mm ³ ; <3.0 – 2.0 x 10 ⁹ /L | <2000 – 1000/mm ³ ; <2.0 – 1.0 x 10 ⁹ /L | <1000/mm ³ ; <1.0 x 10 ⁹ /L |

(a) Definition: A finding based on laboratory test results that indicate increased levels of hemoglobin above normal – i.e. above ULN.

| Metabolism and Nutrition Disorders | | | | |
|---------------------------------------|--|--|--|---|
| Adverse Event | Grade | | | |
| | 1 | 2 | 3 | 4 |

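### For subjects starting below 8.0 g/dL the planned haemoglobin shift table cannot show worsening, and the SAP plans no by-arm count of the protocol's Hb and reticulocyte alerts

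*SAP*

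**What the plan says.** Protocol 8.1, inclusion criterion 4, admits subjects with "Hb of >5.5 and <10.5 g/dL; Hb values within 21 days post-transfusion will be excluded".

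Protocol 7.2 gives laboratory alerts as an example under periodic safety review: "results of blinded laboratory tests will be communicated to the investigator if a subject's absolute reticulocyte count declines to" below 80 × 10⁹/L, if Hb declines below 5.0 g/dL, or on a decline involving 3 g/dL from Day 1 (worded as a decline to, not by, at least that amount).

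SAP 13.5.8.2 states: "Clinical laboratory values will be graded from Grade 1 to Grade 4 using NCI CTCAE, version 5.0". It then plans the shift tables: "Shift tables representing the shift from the baseline grade to maximum NCI-CTCAE Grades (Grade I to IV and Missing) will be provided for selected hematology". Selected chemistry tests are covered too, with one layout for each visit and arm. The anaemia row of SAP Appendix 5 reads:

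- Grade 2: "<10.0 – 8.0 g/dL; <6.2 – 4.9 mmol/L; <100 – 80g/L"
- Grade 3: "<8.0 g/dL; <4.9 mmol/L; <80 g/L; transfusion indicated"
- Grade 4: "Life-threatening consequences; urgent intervention indicated"

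The other Hb row in Appendix 5 concerns increases above normal. Reticulocytes have no row.

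SAP 9.2 lists as a safety endpoint the number and percentage of subjects with "At least one clinically significant change in a laboratory test parameter". SAP Table 9 sets potentially clinically significant (PCS) criteria for hepatic and renal function only. SAP Tables 10 and 11 do the same for vital signs and ECG. All three count unscheduled results.

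**The concern.** The trial enrols people who are already anaemic, and the grading scale runs out of numbers inside the eligible range. Grade 3 has no lower bound and Grade 4 is a clinical description that no Hb value can trigger. For part of the population the shift table is therefore fixed in advance, whatever the drug does to Hb.

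The protocol singles out Hb and reticulocytes for numeric alerts, yet these are the laboratory measures without a subject-level criterion in the SAP. At stake is whether the study report gives a direct count, by arm, of subjects with the haematological falls that the protocol itself watches for.

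**Working it through.** The plan states no figure to reproduce here. The check applies the Appendix 5 limits to the eligible range and then looks for other planned counts.

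**Inputs**

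- Eligible baseline Hb: >5.5 to <10.5 g/dL (Protocol 8.1).
- Grade 3 if <8.0; Grade 2 if 8.0 to <10.0; Grade 1 from 10.0 g/dL to the lower limit of normal (SAP Appendix 5). I assume that this lower limit lies above 10.5 g/dL.
- Hb alerts: <5.0 g/dL, or a fall of at least 3 g/dL from Day 1, which is how I read Protocol 7.2.

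**Step 1: where alert values fall.** The highest value that can meet an alert is below 10.5 − 3.0 = 7.5 g/dL. Every alert value is therefore Grade 3, and whether a shift appears depends only on the baseline grade.

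| Baseline → later value (g/dL) | Fall | Alert met? | Shift table |
|---|---|---|---|
| 7.9 → 4.9 | 3.0 | yes, both | Grade 3 → 3 |
| 7.5 → 4.5 | 3.0 | yes, both | Grade 3 → 3 |
| 6.0 → 3.0 | 3.0 | yes, both | Grade 3 → 3 |
| 5.6 → 4.9 | 0.7 | yes, <5.0 | Grade 3 → 3 |
| 8.0 → 7.9 | 0.1 | no | Grade 2 → 3 |
| 8.0 → 4.9 | 3.1 | yes, both | Grade 2 → 3 |
| 9.0 → 6.0 | 3.0 | yes, fall | Grade 2 → 3 |
| 10.4 → 7.9 | 2.5 | no | Grade 1 → 3 |
| 10.4 → 7.4 | 3.0 | yes, fall | Grade 1 → 3 |

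Below a baseline of 8.0 g/dL no alert-level fall changes the grade. From 8.0 g/dL upward every alert-level fall does, but the table cannot separate 8.0 → 7.9 from 8.0 → 4.9.

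**Step 2: size of the affected band.** As a share of the eligible interval: (8.0 − 5.5) / (10.5 − 5.5) = 2.5 / 5.0 = 50%. As a share of subjects, neither document gives a baseline Hb distribution. Assuming a normal distribution with mean m and SD s, truncated to the eligible range:

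P(Hb < 8.0) = [Φ((8.0 − m)/s) − Φ((5.5 − m)/s)] / [Φ((10.5 − m)/s) − Φ((5.5 − m)/s)]

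| Mean (g/dL) | SD 1.0 | SD 1.25 | SD 1.5 |
|---|---|---|---|
| 7.5 | 68.5% | 64.1% | 60.9% |
| 8.0 | 50.0% | 50.0% | 50.0% |
| 8.5 | 31.5% | 35.9% | 39.1% |
| 9.0 | 17.0% | 23.7% | 29.2% |

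Of the 115 subjects randomized (SAP 8.1.1), this is about 20 (17.0%) to 79 (68.5%). It is the number for whom the shift table is uninformative about Hb falls, not the number expected to reach an alert.

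**Step 3: other planned counts.** Table 9 has no Hb or reticulocyte criterion, Appendix 5 has no reticulocyte row, and no other SAP section counts subjects meeting the Protocol 7.2 alerts.

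**The case against.** The strongest reply is that these falls can be seen elsewhere.

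- **Adverse events.** Under Protocol 11.3.6 the investigator comments on the clinical significance of abnormal results, and significant ones after screening become adverse events. Hb is not on that section's list of blinded tests, and alert-level reticulocytes are passed on. SAP 13.5.8.1 tabulates these events by arm and severity, and a Grade 4 anaemia event can be reported.
- **By-visit summaries.** SAP 13.5.8.2 summarizes haematology values and changes by visit and arm, and SAP 13.0 includes the minimum and maximum.
- **Transfusions and listings.** SAP 13.5.5 counts subjects with at least one red cell transfusion, and all laboratory values are listed.

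It can also be said that the alerts are a communication rule and not endpoints, and that clinical significance in SAP 9.2 may rest on investigator judgement instead of numeric flags. The DMC charter and mock tables are separate documents and could contain such a table.

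Most of this stands. A reader might infer that the plan cannot compare arms on haematological harm, or that a reticulocyte fall would surface only as a favourable mean change in a haemolysis marker. The documents do not support either reading, because the outputs above exist.

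What these outputs lack is a count. By-visit values are those closest to the scheduled day (SAP 10.5), so an unscheduled nadir can drop out. A minimum does not say how many subjects were affected. Under Protocol 12.1.2.2.1 an abnormal result becomes an adverse event only if the investigator judges it significant. Listings give no comparison by arm.

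**Conclusion.** The point holds as a gap in safety reporting. For baselines below 8.0 g/dL the shift table cannot register a laboratory-based fall in Hb; from 8.0 g/dL upward it registers a shift without its depth. The SAP plans no subject-level count, by arm, of the Hb and reticulocyte alerts in Protocol 7.2.

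The band is half of the eligible range. The 17% to 69% of subjects rests wholly on assumed distributions, and nothing in the documents says how many would reach an alert.

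It would go too far to say that any dangerous Hb fall in an eligible subject shows as no shift: alert-level falls from 8.0 g/dL or above always change grade. Communication of alerts to the investigator and DMC oversight are untouched, and so are the primary and key secondary analyses. This is a cheap improvement, not a flaw that threatens the trial's conclusions.

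**What to change.** 1. Have the sponsor reconcile the third alert in Protocol 7.2. It appears to mean a fall of at least 3 g/dL from Day 1, but the text does not say so plainly.
2. In SAP 13.5.8.2 and Table 9, add the number and percentage of subjects by arm with any post-baseline value, unscheduled ones included, meeting each Protocol 7.2 laboratory alert. Present this as descriptive reporting only. It sets no new clinical threshold and no management rule.
3. Keep the CTCAE shift table, with a footnote that Grade 3 is its laboratory ceiling for Hb falls.

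The cost is some SAP wording and one extra table from laboratory data already collected, with no new assessments. Specifying it before unblinding avoids choosing harm criteria after the results are known.

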8.2. Subject Exclusion Criteria

Subjects who meet any of the following criteria will be excluded from the study:

1. Hospital discharge for sickle cell crisis or other vaso-occlusive event within the 4 days prior to randomization (Day 1).
2. Subjects participating in a chronic/prophylactic RBC transfusion program (i.e., regularly scheduled RBC transfusions); any transfusions within 21 days of screening or baseline Hb measurements.
3. Subjects with HbF >25% at screening.
4. Subjects with known active hepatitis A, hepatitis B, or hepatitis C, with active or acute event of malaria, or who are known to be positive for human immunodeficiency virus (HIV).

5. For female subjects of childbearing potential, a positive serum human chorionic gonadotropin (hCG) test (screening) or a positive urine hCG test at randomization (Day 1).
6. Significant kidney disease as indicated by, for example, estimated glomerular filtration rate (eGFR) <45 mL/min as calculated by the equation from the Modification of Diet in Renal Disease (MDRD) Study using creatinine, age, sex, and ethnicity (modified MDRD formula).
7. Alanine aminotransferase (ALT) or aspartate aminotransferase (AST) >3× the upper limit of normal.
8. Body mass index (BMI) <17.0 kg/m² or >35 kg/m²; or total body weight <45 kg.
9. Current or history of malignancies (solid tumors and hematological malignancies), unless the subject has been free of the disease (including completion of any active or adjuvant treatment for prior malignancy) for ≥5 years. However, subjects with the following history of/concurrent conditions are allowed if, in the opinion of the investigator, the condition has been adequately diagnosed and is determined to be clinically in remission, and the subject's participation in the study would not represent a safety concern:
 - a. Basal or squamous cell carcinoma of the skin
 - b. Carcinoma in situ of the cervix
 - c. Carcinoma in situ of the breast
 - d. Incidental histologic finding of prostate cancer (T1a or T1b using the tumor, nodes, metastasis clinical staging system)
10. History of a clinically significant allergic reaction or hypersensitivity, as judged by the investigator, to any drug or any component of the study drug formulations used in the study (see the IB).
11. History of unstable or deteriorating cardiac or pulmonary disease within 6 months before signing the ICF, including but not limited to the following:

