| Hyponatremia (Sodium Decreased) | <LLN - 130 mmol/L | 125-129 mmol/L and asymptomatic | 125-129 mmol/L symptomatic; 120-124 mmol/L | <120 mmol/L; life-threatening consequences |

| Metabolism and Nutrition Disorders | | | | |
|------------------------------------|-------|---|------------------------|---|
| | Grade | | | |
| Adverse Event | 1 | 2 | 3 | 4 |
| | | | regardless of symptoms | |

| Renal and Urinary Disorders | Grade | | | |
|-----------------------------|--|---|---|--|
| Adverse Event | 1 | 2 | 3 | 4 |
| Chronic kidney disease | eGFR (estimated Glomerular Filtration Rate) or CrCl (creatinine clearance) <LLN - 60 ml/min/1.73 m ² or proteinuria 2+ present; urine protein/creatinine >0.5 | eGFR or CrCl 59 - 30 ml/min/1.73 m ² | eGFR or CrCl 29 - 15 ml/min/1.73 m ² | eGFR or CrCl <15 ml/min/1.73 m ² ; dialysis or renal transplant indicated |

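### The SAP's Cockcroft-Gault equation has no sex term, so creatinine clearance in women is overstated and CKD grades near a cut-off could be wrong if they are based on it (minor)

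*SAP*

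**What the plan says.** SAP Section 13.5.8.2 (Laboratory Data) says that "Creatinine clearance are not directly collected and will be calculated using the Crockroft Gault formula". The equation printed there has 140 minus age, multiplied by "Body weight in kg", in the numerator, and 72 multiplied by "serum creatinine in mg/dl" in the denominator. It is given once, for all subjects.

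The rule that explicitly uses this derived quantity is the renal part of Table 9. Its row for "Post-baseline Creatinine Clearance (CREATCLR") flags a value below half of the subject's own baseline. The text introducing the table names only one renal quantity for the summary: "and the renal function parameter (serum creatinine) separately".

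Appendix 5 grades chronic kidney disease on absolute bands that may be read from either measure. The Grade 2 entry is "eGFR or CrCl 59 - 30 ml/min/1.73" m², and the other boundaries are 60 and 15. Grade 1 can also be met through proteinuria or the urine protein/creatinine ratio. Section 13.5.8.2 plans "Shift tables representing the shift from the baseline grade to maximum NCI-CTCAE Grades" for selected hematology and chemistry parameters and refers to Appendix 5 for the criteria.

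The protocol's renal exclusion (Section 8.2, criterion 6) uses an eGFR computed "using creatinine, age, sex, and ethnicity (modified MDRD formula"). eGFR is also a routine chemistry analyte (Protocol 11.3.6.3; listed as GFR in SAP 13.5.8.2).

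**The concern.** The SAP names a formula that conventionally carries a multiplier for women, then prints it without one. Both sexes are enrolled, and the protocol's own screening estimate of kidney function does include sex. The SAP says that it prevails where it differs from the protocol (Section 6.0), so a programmer would code the equation as printed.

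The derived clearance would then be too high in every woman. For any rule that compares it with a fixed cut-off, some women would be placed in a milder category than their kidney function warrants. Appendix 5 contains such cut-offs. A second problem lies beside the first: the printed equation has no body-surface term and so yields mL/min, whereas the Appendix 5 bands are per 1.73 m², and no conversion is given.

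**Working it through.** The plan states no numerical clearance result, so there is no figure to reproduce. The check compares the printed equation with the same equation multiplied by a female factor f.

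**Inputs**
- Printed equation: CrCl = (140 − age) × weight / (72 × serum creatinine), SAP 13.5.8.2.
- Grade boundaries 60, 30 and 15, SAP Appendix 5. Grade 2 is taken as anything from 30 to below 60.
- Table 9 criterion: post-baseline CrCl < 0.5 × baseline.
- Female factor f: **an assumption**, since neither document prints it. The usual value is 0.85; 0.80 to 0.90 is shown as a range.

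**1. Size of the overstatement in women: 1/f − 1**
- f = 0.90: 1/0.90 − 1 = 11.1%
- f = 0.85: 1/0.85 − 1 = 17.6%
- f = 0.80: 1/0.80 − 1 = 25.0%

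**2. Table 9.** The ratio is [f × (140 − age₁) × w₁ / (72 × Cr₁)] / [f × (140 − age₀) × w₀ / (72 × Cr₀)], where 0 is baseline and 1 is post-baseline. The factor f cancels. For a woman of 30 years and 60 kg whose creatinine rises from 0.6 to 1.25 mg/dL:
- as printed: 152.8 falls to 73.3, ratio 0.48
- with f = 0.85: 129.9 falls to 62.3, ratio 0.48

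The flag is the same either way.

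**3. Appendix 5, if the calculated clearance is used.** At cut-off T, a woman's grade changes only if her sex-adjusted value lies between f × T and T. With f = 0.85:
- 60 × 0.85 = 51, so 51 to <60 is reported as 60 to <70.6: Grade 2 reads as Grade 1, or as ungraded, depending on a lower limit of normal that the documents do not give
- 30 × 0.85 = 25.5, so 25.5 to <30 reads as Grade 2 instead of Grade 3
- 15 × 0.85 = 12.75, so 12.75 to <15 reads as Grade 3 instead of Grade 4

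There is also a band just below the lower limit of normal, which cannot be computed for the same reason. Examples in women:

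| Age, weight, creatinine | As printed | × 0.85 | Grade as printed | Grade adjusted |
|---|---|---|---|---|
| 45 y, 55 kg, 1.1 mg/dL | 66.0 | 56.1 | 1 or none | 2 |
| 60 y, 55 kg, 1.0 mg/dL | 61.1 | 51.9 | 1 or none | 2 |
| 60 y, 55 kg, 2.2 mg/dL | 27.8 | 23.6 | 3 | 3 |
| 65 y, 45 kg, 0.8 mg/dL | 58.6 | 49.8 | 2 | 2 |

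First row in full: (140 − 45) × 55 / (72 × 1.1) = 5225 / 79.2 = 66.0, and 66.0 × 0.85 = 56.1. The last two rows show that women away from a cut-off keep their grade.

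**4. Direction of the error in the shift tables.** Baseline and post-baseline values carry the same inflation, so a shift can be lost or created.
- Lost: a true fall from 65 to 55 enters Grade 2. It is reported as 65/0.85 = 76.5 to 55/0.85 = 64.7, with no Grade 2.
- Created: a true fall from 55 to 50 stays within Grade 2. It is reported as 55/0.85 = 64.7 to 50/0.85 = 58.8, an apparent new entry into Grade 2.

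**The case against.** The strongest reply is that no planned table need be wrong. The equation stands directly under Table 9, where the missing factor has no effect. Nothing in the SAP says that the calculated clearance feeds the Appendix 5 grades. Those shift tables are for selected hematology and chemistry parameters; eGFR is in the chemistry panel and clearance is not collected, so the natural reading is that eGFR drives the grade. Appendix 5 also reads as general grading text, since it keeps conditions such as starting steroids, so the mention of clearance there does not prove that it will be used. Finally, the 0.85 is absent from both documents.

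Most of this stands, and it limits the point. It does not remove it. The printed equation is still not the named formula for women, given the usual factor, and Appendix 5 offers two measures with no rule for choosing between them.

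A reader might infer more than the documents support:
- **That CKD grades are too low in women generally.** Only women just below a cut-off change grade, and only if clearance is the measure used. The two lower bands also lie below the eGFR of 45 that the protocol gives as an exclusion example, although that is a different estimator and the values are not interchangeable.
- **That renal worsening is systematically under-reported in women.** The shift error can run either way, as step 4 shows.
- **That Table 9 must change because its clearance row nearly repeats the creatinine row.** At stable weight and age, halved clearance and doubled creatinine are the same event. A near-duplicate flag is a matter of preference and alters no conclusion.

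**Conclusion.** The point holds in a limited form and is minor. The equation in SAP 13.5.8.2 lacks a sex term. Under the assumed factor of 0.85 it overstates clearance in women by about 18% (11% to 25% for 0.90 to 0.80). No Table 9 count changes.

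If, and only if, the calculated clearance is used for Appendix 5, women with a sex-adjusted value of about 51 to <60, 25.5 to <30 or 12.75 to <15 are graded one level too low, baseline-to-maximum shifts can be misstated in either direction, and a quantity in mL/min is held against cut-offs per 1.73 m². The documents give no creatinine distribution, so the number of women affected cannot be derived from them.

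The consequence is confined to descriptive safety tables; no efficacy analysis uses this quantity. It would also be wrong to infer a bias between treatment groups: the same equation applies in every arm, so it does not by itself distort that comparison.

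**What to change.** 1. In SAP 13.5.8.2, add the female multiplier to the printed equation (× 0.85 for female subjects, after checking the constant against the formula's source).
2. In Appendix 5, state that chronic kidney disease is graded on the eGFR already in the chemistry panel. First confirm with the central laboratory that this eGFR is sex-adjusted and reported per 1.73 m². The documents do not settle this: Protocol 11.3.6.3 names no equation, and the exclusion criterion that names one gives its threshold in mL/min.

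Table 9 needs no change. Once the grades rest on eGFR, the added factor alters no specified summary table, but the derived clearance values for women are then correct wherever they are shown. The cost is one factor in the equation, one sentence in Appendix 5 and one query to the laboratory. No new data are needed.
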